6.1.2 Dosing and Administration

mRNA-1273 (0.2 mg/mL) will be diluted in 0.9% NaCl for injection, USP to obtain the specified antigen content in 0.5 mL doses.

mRNA-1273.351 (0.5 mg/mL) will be diluted in 0.9% NaCl for injection, USP to obtain the specified antigen content in 0.5 mL doses.

Each dose will be administered via IM injection into the deltoid muscle.

For Cohort 2, Arms 2A-H, the second dose of vaccine will be administered preferably in the same arm used for the first dose.

For Cohort 2, Arms 2A and 2B, the third dose of vaccine will also be administered preferably in the same arm used for the first dose.

The pharmacist will prepare a single dose for each subject based on cohort assignment.

See the protocol-specific Manual of Procedures (MOP) for detailed information on the preparation, labeling, storage, and administration of vaccine for each cohort. Vaccine preparation will be performed by the participating site's research pharmacist on the same day of vaccine administration to the subject.

Visually inspect the mRNA-1273 and mRNA-1273.351 upon receipt and prior to use. If the study product(s) appear(s) to have been damaged, contaminated or discolored, contain(s) visible particulate matter, or if there are any concerns regarding the integrity, do NOT use the affected study product(s). The affected study product(s) must be quarantined at appropriate storage temperature and labeled as 'Do Not Use' (until further notice). The participating site PI or responsible person should immediately contact the DMID Product Support Team at [contact] and DMID Clinical Project Manager for further instructions before any additional vaccinations are administered. Based on the information collected, DMID and/or the manufacturer will determine whether the affected study product(s) can be used. If the affected study product(s) cannot be used, the participating site will receive specific instructions on how to return the affected study product(s) to the DMID Clinical Material Services (CMS) or destroy the affected study product(s) on-site. If the study product is unusable, study staff will use another vial from the study supply. Replacement vials may be requested by contacting DMID. Additional instructions for quarantine and DMID contact information are provided in the protocol-specific MOP.

The injection dose volume (0.5 mL each) of vaccine should be withdrawn from the final mixed vial(s) or compounding vial(s) containing the prepared dosing solution. The number of individual dosing syringes that may be filled from one mixing vial varies depending on the dosage. Doses for multiple subjects may be drawn into individual dosing syringes from the same final mixed vial within 30 minutes of completion of dosing solution preparation. Gently invert the final mixed vial(s) or the compounding vial(s) 20 times until components are mixed prior to withdrawing. **Do not mix vigorously or sonicate or vortex.**

Aseptic technique will be used for the withdrawal and administration of each dose of vaccine using a disposable, sterile needle appropriate in length for each subject and a 1-mL disposable, sterile syringe.

The expiration time of the dosing syringe containing the prepared study vaccine is 8 hours at room temperature after the solution is drawn into the dosing syringe.

6.1.3 4.1Dose Modifications

No dose modifications.

6.2 Accountability/Handling/Storage/Preparation

6.2.1 Acquisition and Accountability

Product: mRNA-1273 and mRNA-1273.351

Will be provided by ModernaTX, Inc. via the DMID CMS.

Upon request by DMID, study product will be transferred to the following address:

DMID Clinical Materials Services Contract
Fisher BioServices
[name]
[name]
[contact]
[contact]

Email: [contact]

Diluent: 0.9% NaCl for injection, USP

Will be provided by DMID via the DMID CMS.

All study products will be shipped to the clinical research site upon request and approval from DMID.

Accountability

The participating site PI is responsible for study product distribution and disposition and has ultimate responsibility for study product accountability. The participating site PI may delegate to the participating site's research pharmacist responsibility for study product accountability. The participating site's research pharmacist will be responsible for maintaining complete records and documentation of study product receipt, accountability, dispensation, storage conditions, and final disposition of the study product(s). Study product accountability records and dispensing logs should include, but are not limited to the following: DMID protocol number; name, dosage form, strength of the study product; capture vial numbers assigned sequentially by the pharmacists as vials/syringes are used (number uniquely, do not start over at 1 or repeat numbers), manufacturer or other source; control, lot number or other identification number; expiration or retest date; date of receipt of the study product; quantity received from supplier; subject identification number; quantity dispensed as amount or dose per subject; balance of study product currently available; disposition of study product if not dispensed to a study subject (e.g., disposed/destroyed or returned to supplier as per protocol or protocol-specific MOP or as directed by DMID); date of vaccine preparation/administration, time of vaccine preparation, expiration of vaccine preparation; and amount of vaccine withdrawn for administration. Time of vaccine administration to the subject will be recorded on the appropriate data collection form (DCF). All study product(s), including the amount of study product, diluent (0.9% NaCl for injection, USP), and vial admixtures, whether administered or not, must be documented on the appropriate study product accountability record or dispensing log. The sponsor's monitoring staff will verify the participating site's study product accountability records and dispensing logs per the DMID-approved clinical monitoring plan (CMP).

Once all subject dosing is complete, the pharmacy staff should retain or dispose of used study products and complete study product accountability procedures in accordance with site-specific standard operating procedures (SOPs). This applies to:

- used and unused mRNA-1273 or mRNA-1273.351 vials
- used mixing vials
- mRNA-1273 or mRNA-1273.351 cartons

All used supplies noted above may either be sequestered from the unused supplies and retained until study conclusion or until study product accountability has occurred by the monitor and written notification stating retention is no longer required is received, or may be destroyed in accordance with site-specific SOPs with a second pharmacy staff member's observation and verification as documented in the pharmacy log. Refer to the protocol-specific MOP for details on storing used study product vials, used 0.9% NaCl Injection vials and used mixing vials.

Destruction

After the study treatment period has ended or as appropriate over the course of the study after study product accountability has been performed, disposition of unused and used study product vials should occur as noted:

- Unused and used study product vials:
 - Should be destroyed on-site following applicable site procedures or by the site's selected destruction vendor. Following the site's procedure for the destruction of hazardous material or study product destruction policy/SOP when destroying used and unused items.
 - A certificate of destruction or documentation of destruction should be provided to the sponsor and retained in the Pharmacy Binder once completed.
- Used syringes may be destroyed in accordance with site-specific SOPs.

6.2.2 Formulation and Appearance

Product: mRNA-1273 and mRNA-1273.351

mRNA-1273 is provided as a sterile liquid for injection, white to off-white dispersion in appearance.

mRNA-1273.351 is provided as a sterile liquid for injection, white to off-white dispersion in appearance.

Diluent: 0.9% NaCl for injection, USP

The USP grade 0.9% NaCl or normal saline for injection is a sterile, nonpyrogenic, isotonic solution; each mL contains NaCl 9 mg. It contains no bacteriostatic agent, antimicrobial agent, preservatives, or added buffer and is supplied only in single-dose containers. It is clear in appearance, and available in 10 mL vials.

Each of the study products will be labeled according to manufacturer specifications and include the statement "Caution: New Drug Limited by Federal Law to Investigational Use."

Sterile empty vials (2-mL or 10-mL) will be provided with latex-free stoppers.

6.2.3 Product Storage and Stability

Product: mRNA-1273 and mRNA-1273.351

mRNA-1273 vials are stored frozen between -25° to -15°C. Vials can be stored refrigerated between 2° to 8°C for up to 30 days prior to first use. Unpunctured vials may be stored between 8° to 25°C for up to 12 hours. Do not refreeze. Store in the original carton to protect from light.

mRNA-1273.351 vials are stored frozen between -60°C to -90°C. Stability and compatibility with the apparatus intended for administration for up to 8 hours after preparation were assessed. The prepared doses were stable for clinical in-use for up to 8 hours at room temperature. Store in the original carton to protect from light.

Diluent: 0.9% NaCl for injection, USP

0.9% NaCl for injection, USP is stored at 20 to 25°C (68 to 77°F). [See USP Controlled Room Temperature.]

The temperature of the storage unit must be manually recorded daily (excluding non-business days and holidays, as applicable) and continuously monitored and recorded during the course of this trial per site-specific SOPs, and documentation will be maintained. If the temperature fluctuates outside of the required range, the affected study product(s) must be quarantined at the correct storage temperature and labeled as 'Do Not Use' (until further notice). The participating site's research pharmacist must alert the participating site PI and study coordinator, if the temperature fluctuates outside of the required range. In the event the temperature fluctuates outside of the required range, including accidental deep-freezing or disruption of the cold chain, the affected study product(s) must not be administered. The participating site PI or responsible person should immediately contact the DMID Product Support Team at [contact] for further instructions before any additional vaccinations are administered. Based on the information collected, DMID and/or the manufacturer will determine whether the affected study product(s) can be used. If it cannot be used, the participating site will receive specific instructions on how to return the affected study product(s) to the DMID CMS or destroy it on-site. Additional instructions for quarantine and DMID contact information are provided in the protocol-specific MOP.

mRNA-1273 and mRNA-1273.351 must be stored in a secure area with limited access (pharmacy staff only), and must be stored frozen. The freezer should have an automated temperature recording and alert system. There must be an available back-up freezer. The freezers must be connected to a back-up generator; or alternate plan in the event of a power failure. The pharmacy must have in place a 24-hour alert system that allows for rapid response in case of freezer malfunctioning. In addition, vaccine accountability study staff (e.g., pharmacy staff) are required to keep a temperature log to establish a record of compliance with these storage conditions. Only vaccine accountability study staff (e.g., pharmacy staff) should have access to the product used in this study. The participating site is responsible for reporting any mRNA-1273 and mRNA-1273.351 that was not temperature controlled during shipment or during storage to the pharmacy staff. Such mRNA-1273 and mRNA-1273.351 will be retained for inspection by the pharmacy staff and disposed of according to approved methods.

6.2.4 Preparation

Refer to the protocol-specific MOP for details about preparation.

6.3 Measures to Minimize Bias: Randomization and Blinding

6.3.1 Treatment Assignment Procedures

Per International Council for Harmonisation of Technical Requirements for Pharmaceuticals for Human Use (ICH) guideline E6: GCP, screening records will be kept at the participating site to document the reason why an individual was screened, but failed trial entry criteria. The reasons why individuals failed screening will be recorded in the Statistical and Data Coordinating Center's (SDCC) Advantage eClinicalSM (Electronic Data Capture System).

Once consented and upon entry of demographic data and confirmation of eligibility for this trial, the subjects will be enrolled.

6.3.2 Randomization and Blinding

Subjects in Cohort 1 will be stratified by DMID 20-0003 cohort (age and dosage group) and randomized 1:1 to Arm 1A or 1B. Subjects in Cohort 2 will be randomized in a ratio of 3:3:4:4:4:4:4:4 for Arms 2A-H. Randomization will be done in the SDCC's Advantage eClinicalSM (Electronic Data Capture System).

6.3.3 Blinding and Masking Procedures

This study is unblinded.

6.4 Study Intervention Compliance

Each dose of study product will be administered by a member of the clinical research team that is qualified and licensed to administer the study product. Administration and date, time, and location of injection will be recorded on the appropriate DCF.

6.5 Concomitant Therapy

Concomitant medications include only prescription medications and vaccines received outside of the study taken by the subject at the time of enrollment through 28 days after the last vaccination. At each study visit, if there are new SAEs, Protocol Specified AESIs, MAAEs, or NOCMCs, concomitant medications should be recorded on the appropriate DCF.

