16. Receipt of any other SARS-CoV-2 vaccine or any experimental coronavirus vaccine at any time prior to or during the study, except Cohort 1 subjects who received mRNA-1273 in DMID 20-0003.
17. Close contact of anyone known to have SARS-CoV-2 infection within 14 days prior to vaccine administration.
18. History of COVID-19 diagnosis, positive SARS-CoV-2 PCR test, or, for Cohort 2 only, a known positive SARS-CoV-2 serologic test.
19. On current treatment with investigational agents for prophylaxis of COVID-19.

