7.1.3 Discontinuation of Study Intervention

For Cohort 2, Arms 2A-H, prior to receiving the second vaccination, and, for Arms 2A and 2B, prior to receiving the third vaccination, subjects will be reassessed. The following events constitute contraindications to any further administration of study vaccines. If any of these events occur during the study prior to the second vaccination, the subject must not receive the second vaccination but will be encouraged to continue study participation for safety and immunogenicity evaluations through 12 months after their last vaccination. For Cohort 2, Arms 2A and 2B, if any of these events occur after the second vaccination and before the third vaccination the subject must not receive the third vaccination but will be encouraged to continue study participation for safety and immunogenicity evaluations through 12 months after their last vaccination.

- Any clinically significant medical condition that, in the opinion of the participating site PI or appropriate sub-investigator, poses an additional risk to the subject if he/she continues to participate in the study.
- Confirmed SARS-CoV-2 infection.
- Anaphylaxis or unexpected systemic hypersensitivity reaction following the administration of a prior study vaccination.
- Any SAE judged to be related to vaccine.
- Pregnancy.
- New information becomes available that makes further participation unsafe or interferes with the evaluation of responses.
- Termination of this trial.

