8.3.1.2 Unsolicited Adverse Events

All AEs spontaneously reported by the subject and/or in response to an open question from study staff or revealed by observation, physical examination or other diagnostic procedures must be recorded on the appropriate DCF.

Unsolicited AEs of all severities will be reported from the time of study product administration through 28 days post last vaccination.

After 28 days post last vaccination through the end of study, only SAEs, Protocol Specified AESIs, MAAEs, and NOCMCs (as detailed in [Section 8.3.2](#)) will be reported as AEs.

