8.3.9 Adverse Events of Special Interest (AESIs)

Adverse Events of Special Interest (AESIs) represent any events for which additional data (besides the standard AE data) are desired. An adverse event of special interest (serious or nonserious) is one of scientific and medical concern specific to the sponsor's product or

program, for which ongoing monitoring and rapid communication by the investigator to the sponsor is required. Such an event may require further investigation in order to characterize and understand it. Depending on the nature of the event, rapid communication by the trial sponsor to other parties (e.g., regulators) may also be required. These may be at the request of the regulatory agency, industry partner or DMID, and driven by a regulatory requirement, or known or potential risk from the product or class. Non-structured data similar to SAEs will be collected for AESIs. AESIs encompass the following terms:

- Protocol Specified AESIs: See [Section 12](#), Appendix A.
 - All suspected cases of anaphylaxis should be recorded. For reporting purposes, a participant who displays signs/symptoms consistent with anaphylaxis should be reported as a potential case of anaphylaxis.
 - All suspected cases of myocarditis or pericarditis should be recorded. For reporting purposes, a participant who displays signs/symptoms consistent with myocarditis or pericarditis should be reported as a potential case of myocarditis or pericarditis.
- NOCMCs – defined as any new ICD diagnosis (per current International Statistical Classification of Diseases and Related Health Problems) that is applied to the subject during the course of the study, after receipt of the study agent, that is expected to continue for at least 3 months and requires continued health care intervention.
- MAAEs – defined as a hospitalization, emergency room visit or an otherwise unscheduled visit to or from medical personnel for any reason; and considered related to study product.

All AESIs are assessed, recorded, and followed as described above under AEs. AESIs that meet SAE criteria will be reported on an SAE form within 24 hours to the DMID Pharmacovigilance Group, at the following address:

DMID Pharmacovigilance Group
Clinical Research Operations and Management Support (CROMS)
[name]
[name]
SAE Hot Line: [name] (US) or [name] (outside US)
SAE [contact] (US) or [name] (outside US)
SAE Email Address: [contact]

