9.3 Populations for Analyses

The Safety Analysis population for the study includes all subjects who received one dose of study vaccine. Analyses for the safety population will include safety reported through the end of the study. The modified intent-to-treat (mITT) population includes all subjects who received at least one dose of vaccine and contributed both pre- and at least one post-vaccination venous blood sample for immunogenicity testing for which valid results were reported.

In the final analysis, protocol deviations will be reviewed to determine which protocol deviations may affect the analysis. The per protocol (PP) population will then be defined – and this includes all subjects in the mITT subset with the following exclusions:

- Data from all available visits for subjects found to be ineligible at baseline.
- Data from all visits subsequent to the protocol deviations that are considered to affect the science.
- Data from any visit that occurs substantially out of window.

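### Outside COVID-19 vaccination and uncomplicated infection need no dated record beyond 28 days after the last dose, yet the 3-, 6- and 12-month titres enter the mITT summaries

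*Protocol*

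**What the plan says.** **Collection.** Section 6.5 records prescription medicines and "vaccines received outside of the study taken by the subject at the time of enrollment through 28 days after the last vaccination". The concomitant-medication rows of Tables 3, 4 and 5 stop at the same point (Days 29, 85 and 57). For later visits, 6.5 adds: "At each study visit, if there are new SAEs, Protocol Specified AESIs, MAAEs, or NOCMCs, concomitant medications should be recorded on the appropriate DCF".

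**Events.** Section 8.3.1.2 narrows reporting at the same time: "After 28 days post last vaccination through the end of study, only SAEs, Protocol Specified AESIs, MAAEs, and NOCMCs" are reported. An MAAE, by section 8.3.9, must be a medical visit "and considered related to study product".

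**Follow-up.** Under section 7.1.3, a Cohort 2 subject with confirmed infection before a remaining dose gets no further study vaccine but "will be encouraged to continue study participation for safety and immunogenicity evaluations through 12 months after their last vaccination".

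**Analysis.** Section 9.4.3 presents seroconversion, GMFR and GMT by arm at all timepoints for the mITT population, which "includes all subjects who received at least one dose of vaccine and contributed both pre- and at least one post-vaccination venous blood sample" with valid results (9.3). The per-protocol set removes "Data from all visits subsequent to the protocol deviations that are considered to affect the science", among other exclusions. By 9.4.3 that analysis is optional.

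**The concern.** The secondary objective is the humoral response to the study vaccines in naïve and previously vaccinated people. A later infection or an outside COVID-19 vaccine can raise titres for reasons unrelated to the assigned regimen. If such exposures are pooled into the late summaries, the 3-, 6- and 12-month GMT and GMFR run high and waning looks slower than it is. A subject whose titre has fallen back towards baseline could also count as a 4-fold responder because of the exposure alone.

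Collection matters more here than analysis. An SAP can define how to treat samples after an exposure, but it cannot apply that rule without dates. The protocol fixes what sites are required to collect.

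**Working it through.** The protocol gives no exposure rate and no fold-rise after exposure, so there is no stated figure to reproduce.

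**Step 1: serum drawn after routine recording ends.** Study days come from Tables 9 to 11 and the end of recording from section 6.5.

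| Arms | Recording ends | Later serum draws | Share of all draws | Follow-up remaining |
|---|---|---|---|---|
| 1A–1B | Day 29 | Days 91, 181, 366 | 3 of 6 | 366 − 29 = 337 days |
| 2A–2B | Day 85 | Days 147, 237, 422 | 3 of 10 | 422 − 85 = 337 days |
| 2C–2H | Day 57 | Days 119, 209, 394 | 3 of 8 | 394 − 57 = 337 days |

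The serum rows of Tables 4 and 5 appear to leave the 12-month visit unmarked, while Tables 10 and 11 list 16 mL there. The count follows Tables 10 and 11. On the other reading, Cohort 2 has two late draws per arm.

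**Step 2: what the protocol would capture after that point.**
- *Outside COVID-19 vaccine.* It is no longer a routine concomitant medication. It breaches exclusion criterion 16, so it is reportable as a deviation under 10.1.10 if the site learns of it. No question that would reveal it is required.
- *Uncomplicated infection.* By itself it is not an SAE, a listed AESI or a chronic condition, and a visit for community COVID-19 would not normally be judged product-related. A case with a concept listed in Appendix A, such as anosmia or ageusia, is captured.
- *Interim history (8.2).* It is taken at the late visits and notes changes, but the only targets it names are AESIs, MAAEs and NOCMCs.

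**Step 3: what the analysis would remove.** mITT removes nothing for exposure. The per-protocol rule can drop visits after an outside vaccination treated as a deviation. Infection is not non-compliance, so the rule does not clearly reach it.

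**Step 4: size, under stated assumptions.** Let a fraction f of an arm be exposed by a visit, and let exposure multiply the titre by k. The shift in mean log10 titre is f × log10(k), so the GMT is inflated by k^f. GMFR is inflated by the same factor, because baseline is unchanged.
- f = 10%: 5^0.1 = 1.17; 20^0.1 = 1.35
- f = 30%: 5^0.3 = 1.62; 20^0.3 = 2.46

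The ratio of a late GMT to an unaffected peak GMT is raised by the same factor, which is how waning is understated.

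At f = 10%, the chance that an arm contains at least one exposed subject is 1 − 0.9^n: 79% for n = 15, 88% for n = 20 and 96% for n = 30.

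**The case against.** The best reply is that the protocol is not silent and that the rest belongs in the SAP. Several parts of it stand.

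- A reader might infer that outside exposure is neither recorded nor removed at all. The text does not support that. Exclusion 16, deviation reporting, the interim history and the AESI list each catch some cases, and the per-protocol set can drop visits after an outside vaccination.
- A reader might infer that all the immunogenicity results are affected by missing records. The 14- and 28-day samples after each dose fall inside the recording window, so the gap in collection touches only the last draws in each arm.
- A reader might infer that the damage could never be repaired. Serum for secondary research is drawn at each venipuncture visit and stored indefinitely, so some later serology is possible. However, section 8.1.2 names no infection-specific assay, and a titre alone does not date an exposure.
- A reader might infer spurious differences between regimens. With f = 30%, k = 10 and 20 per arm, one SD of chance imbalance is √(0.3 × 0.7 × 2/20) = 0.145 on the log10 scale, a ratio of 1.40. Between randomised arms this is sampling error, which also widens the confidence intervals, and the trial tests no hypothesis. It is not evidence of bias between arms.
- For Cohort 2, exclusion 18 bars only "for Cohort 2 only, a known positive SARS-CoV-2 serologic test", so a reader might infer a flaw in the naïve population. The protocol consistently describes people with no known history, and the mandatory Day 1 serum allows baseline serostatus to be established later. Nothing is lost by leaving this to the SAP.

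An all-samples mITT summary is also a legitimate treatment-policy choice. None of this answers the collection gap: sites that follow the protocol exactly need not ask about, or date, the exposures that any later rule would depend on.

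**Conclusion.** The point holds in a limited form. Systematic recording of outside vaccines ends 28 days after the last vaccination, uncomplicated infection is not reportable after that, and the late titres enter an mITT analysis with no exposure rule. The only removal route is optional and does not clearly cover infection.

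The direction is upward for late GMT, GMFR and seroconversion, with waning understated. The size is unknown: 1.17- to 1.35-fold at 10% exposed with a 5- to 20-fold rise is an illustration, since neither input comes from the protocol. It also assumes that the other safeguards miss these cases and that k is a common multiplier. The primary safety endpoint is not touched by this point. The change is worth making because it is cheap and dates not collected prospectively may not be recoverable.

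**What to change.** 1. In section 6.5 and Tables 3 to 5, require each visit through 12 months after the last dose to record any outside COVID-19 vaccine and any confirmed SARS-CoV-2 infection, with dates. The interim-history visits already scheduled can carry both questions.
2. In sections 9.3 and 9.4.3, present GMT, GMFR and seroconversion excluding samples taken after the first such event, alongside the all-samples mITT results, and give the number of subjects affected by arm and visit.
3. Leave any flag for Cohort 2 subjects seropositive on the Day 1 serum to the SAP.

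The cost is two extra questions per visit and fewer late samples in the restricted analysis, which matters with 15 to 20 subjects per Cohort 2 arm. Infections that are never diagnosed would still be missed, so the restricted analysis reduces the bias and may not remove it.
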